1.0 SUMMARY OF STUDY (Abstract with a maximum of 300 words)

The ideal local anesthetic (LA) solution for activation of a labor epidural would be one that provides rapid pain relief with minimal side effects such as hypotension and motor blockade. Commonly used LA in obstetrics includes bupivacaine and lidocaine. Due to either slow onset (bupivacaine)¹ or a higher incidence of hypotension (lidocaine)² neither meet the criteria for the ideal LA. This is where the thought of combining the two LA solutions arises. Maybe a 1:1 mix will produce a faster onset than bupivacaine with a lower incidence of hypotension than lidocaine.

We hypothesize that lidocaine will achieve a T₁₀ level the fastest when compared to bupivacaine and bupivacaine plus lidocaine. The bupivacaine plus lidocaine onset of action will not be significantly faster when compared to bupivacaine. Given the concentration of the bupivacaine, less hypotension and motor block will be present when compared to the lidocaine and bupivacaine plus lidocaine. The bupivacaine plus lidocaine will offer no increased benefit of having a faster onset with less hypotension or motor blockade than either LA solution alone.

We will conduct a prospective, randomized, double-blind study on 45 patients receiving a lumbar epidural for labor analgesia. After a negative test dose, the anesthesia provider will administer the randomized LA via epidural catheter: 10 mL 0.125% bupivacaine, or 10 mL 1% lidocaine, or 5 mL 0.125% bupivacaine plus 5 mL 1% lidocaine. The investigator will assess the patients sensory level to pin prick and ice, degree of motor block, blood pressure, heart rate, and fetal heart rate at intervals of 0, 5, 10, 15, and 20 minutes. Primary outcome will be the time to achieve a T₁₀ level. Secondary outcomes include the total spread of the block, onset and degree of motor block, incidence of hypotension and need for vasopressor therapy, and fetal well-being.

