4.0 OBJECTIVE(S) & HYPOTHESIS

Our overall goal is to determine which commonly used LA or combination of LA demonstrates the most ideal properties in a patient receiving an epidural for labor pains. As anesthesiologists, we strive to provide a fast-acting and safe anesthetic in these patients to elicit rapid pain relief in laboring mothers.

Currently, there are several ways in which we activate a labor epidural with LA. Three of the more common LA solutions used are 1% lidocaine, 0.125% bupivacaine, or a combination of bupivacaine and lidocaine. In a prospective, randomized, double-blinded study, we plan to determine if one solution is more superior to the others.

Briefly, after consent is obtained, a standard anesthesia provider will place a labor epidural in regular fashion. After a negative test dose, the anesthesia provider will then administer the study solution the patient was randomized to receive (10 mL of 0.125% bupivacaine, 10 mL of 1% lidocaine, or 5 mL of 0.125% bupivacaine plus 5 mL of 1% lidocaine). The standard epidural infusion bag will then be started by the anesthesia provider. Both the patient and investigator will be blinded to the study. Once the study drug bolus has been given, the investigator will collect the data.

Data to be collected will be: sensory level (by pin prick and ice), degree of motor block by using a modification of Bromage's scale³ (see section 8.0), maternal heart rate (HR) and blood pressure (BP), the need to administer a vasopressor agent (phenylephrine or ephedrine) to treat hypotension, the amount of vasopressor given, and fetal heart rate (FHR). Starting with the initial bolus (Time 0 or T₀), data will then be collected 5, 10, 15, and 20 minutes after the bolus.

The primary outcome for this study is the time it takes to achieve a T₁₀ dermatome level by pinprick (which signifies an adequate epidural level for labor analgesia).

Secondary outcomes include: the total spread (both cephalad and caudal) of the LA (dermatome level to be determined by pin prick and ice), degree of motor block, incidence of maternal hypotension defined as a BP >20% decline from baseline, the need to administer a vasopressor to treat the hypotension, the amount given, and if there is any change in fetal status by monitoring FHR.

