We hypothesize that lidocaine will achieve a T₁₀ level the fastest when compared to bupivacaine and bupivacaine plus lidocaine. The bupivacaine plus lidocaine solution's onset of action will not be significantly faster when compared to bupivacaine. Given the concentration of the bupivacaine, less hypotension and motor block will be present when compared to the lidocaine and bupivacaine plus lidocaine. The bupivacaine plus lidocaine will offer no increased benefit of having a faster onset with less hypotension or motor blockade than either LA solution alone.

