5.0 INTERPRETATION OF EXPECTED RESULTS

06_18_2014

If we see a significant decrease in time to achieve a T₁₀ dermatome level with the bupivacaine and lidocaine mixture compared to the bupivacaine only solution, then that would imply that the addition of the lidocaine did speed up the onset of action of the LA solution we used to activate the epidural. We would also need to account for each LA solution's side effect profile. By measuring the incidence of hypotension and degree of motor blockade, we will be able to determine if one solution's side effect profile is more favorable. By determining the advantages vs. disadvantages of each solution, we would be able to recommend the most ideal LA solution of those studied as the solution best suited for activation of labor epidurals.

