8.0 STUDY INTERVENTIONS/PROCEDURES

Our study will be a prospective, randomized, double-blind study comparing three commonly used methods to activate a labor epidural. These three solutions will be 10 mL of 0.125% bupivacaine (B), 10 mL of 1% lidocaine (L), and 5 mL of 0.125% bupivacaine plus 5 mL of 1% lidocaine (BL). The primary outcome of the study will be measurement of the time it takes to achieve an adequate anesthetic level (T₁₀) to control labor pains. Secondary outcomes include: the total level achieved, degree of motor blockade, incidence of maternal hypotension (>20% decline from baseline), the need for vasopressor use, the amount of vasopressor needed, and fetal

well-being (monitoring of FHR). Since LA will be required to produce our primary outcome, no group will receive a placebo. The three groups (B), (L), and (BL) will be compared to each other.

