11.0 STATISTICAL CONSIDERATIONS

The outcome Y is time to T_{10} sympathectomy. An ANOVA will be used to estimate the overall difference of the mean onset times between study groups. An estimate of onset times of 5, 6 and 7 minutes and an estimated variance of 1 min is based on the existing literature.¹² Using an alpha = 0.05, 80% power and a calculated effect size of $f = 0.82$, the total sample size sample size based on an ANOVA is N=18. Accounting for some prediction inaccuracy, we propose a target sample size of N=45, n=15 per study group.

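### The hypothesis that the mixture is not significantly faster than bupivacaine is met by any non-significant result, and the plan has no estimate, interval or rule to tell no gain from an inconclusive finding

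*Combined protocol and SAP*

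**What the plan says.** Section 1.0 states the prediction as "The bupivacaine plus lidocaine onset of action will not be significantly faster when compared to bupivacaine", and section 4.0 repeats it almost word for word: the mixture's "onset of action will not be significantly faster when compared to bupivacaine". Section 4.0 adds that the mixture will offer "no increased benefit of having a faster onset with less hypotension or motor blockade than either LA solution alone". Neither section gives a size of difference that would count as a gain.

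Section 5.0 (Interpretation of Expected Results) gives one reading rule for this pair. If the mixture shows a significant decrease in time to T10 against bupivacaine, "then that would imply that the addition of the lidocaine did speed up the onset of action". It says nothing about a non-significant result. It then says that, after weighing advantages and disadvantages, "we would be able to recommend the most ideal LA solution of those studied".

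Section 8.0 says "The three groups (B), (L), and (BL) will be compared to each other". Section 11.0, the only statistical section, says "An ANOVA will be used to estimate the overall difference of the mean onset times between study groups". It names no pairwise test, pairwise estimate, confidence interval, multiplicity rule or margin.

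On measurement, section 4.0 says "data will then be collected 5, 10, 15, and 20 minutes after the bolus", and section 8.0 repeats that schedule. No section says how a T10 time between two readings is assigned.

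**The concern.** The hypothesis predicts the outcome of a significance test, not the size of an effect. A trial too imprecise to see a real gain confirms it just as well as a trial that shows there is none. The null is also the result the authors expect for this pair, and it is the one result for which the plan has no reading rule.

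BL versus B is central to the trial's purpose, because section 2.0 asks whether the combination has any distinct advantage over the single agents. Without a prespecified estimate and interval, a reader of the eventual report could not tell a missed gain from a true absence of gain. The same weakness affects the parts of the hypothesis about hypotension and motor block, which are also phrased as no benefit without a size.

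**Working it through.** **Inputs.** From section 11.0: means 5, 6 and 7 minutes, variance 1 (so SD 1 minute), alpha 0.05, 15 per arm. Section 11.0 does not say which arm has which mean. Section 4.0 predicts lidocaine (L) fastest, which fits L = 5. Taking BL = 6 and B = 7 is an assumption. Tests are two-sided.

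**1. The plan's own figure.** f = √[((5−6)² + 0 + (7−6)²)/3] / 1 = √(2/3) = 0.816. The noncentral F distribution gives power 80.5% at N = 18 (80.9% with f = 0.82) and 77.5% at N = 17. So N = 18 is correct for the overall test. At N = 45 the noncentrality is 45 × 2/3 = 30 and power is 99.9%.

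**2. What the overall test says about BL versus B.** Take means L/BL/B = 5/7/7, with no BL–B difference. Then f = 0.943, and power at N = 45 is still above 99.9%. A significant ANOVA can come from lidocaine alone.

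**3. BL versus B with exact timing.** The standard error is √(2/15) = 0.365 minutes. For a true 1-minute gain the noncentrality is 1/0.365 = 2.74.
- Two-group t test (28 df): power 0.753, so non-significant in 24.7%.
- Pooled SD from three arms (42 df): power 0.763, so non-significant in 23.7%.
- 95% CI half-width: 2.048 × 0.365 = 0.75 minutes (two-group) or 2.018 × 0.365 = 0.74 (pooled).

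For example, an observed gain of 0.70 minutes would have a CI of about −0.05 to 1.45. That meets the hypothesis as worded, yet it is compatible with a gain larger than the plan's own 1-minute step.

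**4. BL versus B if times are rounded up to the next reading.** This rule is an assumption. With normal times and SD 1, the chance of being recorded at 5 minutes is Φ(5 − mean): 84% for mean 4, 50% for 5, 16% for 6 and 2% for 7. Means 6 and 7 therefore look similar on the grid (16% against 2%), while 5 and 6 do not (50% against 16%). Simulated share of non-significant BL-versus-B results (200,000 trials per row):

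| L/BL/B means | True BL gain | Two-group t | Pooled SD |
|---|---|---|---|
| 5/6/7 | 1 min | 85% | 94% |
| 4/5/6 | 1 min | 46% | 40% |
| 5/5/6 | 1 min | 46% | 51% |
| 5/6/6 | none | 96% | 98% |
| 5/7/7 | none | 99.9% | 100% |

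At 5/6/7 the overall ANOVA is significant in 86% of trials. In 72% (two-group) or 80% (pooled) of trials it is significant while BL versus B is not.

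**5. How much a null tells the reader.** This is the probability of a null with no gain, divided by its probability with a 1-minute gain.
- Exact timing: 0.95/0.247 = 3.8 to 0.95/0.237 = 4.0.
- Rounded up, gain at 4/5/6, two-group test, null at 4/5/5: 0.954/0.459 = 2.1.
- Rounded up, gain at 5/6/7: from 0.977/0.936 = 1.04 to 0.9995/0.846 = 1.18.

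**The case against.** The prediction in section 4.0 is a hypothesis, not a decision rule. The stated aim there is to find whether one solution is superior, and section 5.0 (Interpretation) bases the recommendation on weighing advantages against disadvantages, not on a null for this pair. This stands. A reader might infer that the trial plans to report a null as proof of no benefit, but no section says so. A reader might also infer that BL versus B was left out. It was not, because sections 5.0 (Interpretation) and 8.0 intend it. Only its specification is missing.

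The size of the problem is also open to challenge. The highest miss rates need both BL and B means inside the 5-to-10-minute interval and a rounding rule that the documents do not state. The same 1-minute gain placed one minute earlier is missed in 46% or 40% of trials, not 85% or 94%. With exact timing the miss rate is close to that of an ordinary 80%-power design, and a null then carries some information. This stands too. The inference that a null is the likely result even if BL is faster, or that it has almost no evidential value, holds only for some placements of the means on the grid.

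Neither argument supplies the missing reading rule. Even in the most favourable case, exact timing, about one trial in four would meet the hypothesis although BL is faster by the plan's own step.

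**Conclusion.** The concern holds as a gap in specification and wording. The hypothesis counts an imprecise null as confirmation, and the plan provides no BL-versus-B estimate, interval or rule that would show the difference.

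The size is conditional on SD 1 minute, 15 per arm, a true 1-minute gain and an assumed assignment of means to arms. It is 24–25% missed gains with exact timing, and about 40–94% if times are rounded up to the 5-minute readings. The sample-size arithmetic for the overall ANOVA is correct and is not part of this point. The trial can run as designed, but the text should be changed before the data are analysed, because the result it predicts could not otherwise be interpreted.

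**What to change.** **Section 11.0.** Name B minus BL onset time as a prespecified comparison, reported as an estimate with a 95% CI. State how the T10 time is recorded. If it is recorded only at the 5-minute readings, use a method that respects them, such as an interval-censored model, and not a t-interval on rounded times.

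**Sections 1.0, 4.0 and 5.0 (Interpretation).** Reword the hypothesis as one about the size of the B minus BL difference. State that a non-significant difference will be reported with its CI as inconclusive about benefit, not as evidence of no benefit. Apply the same rule to hypotension and motor block.

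**Optional margin.** A conclusion that BL is not meaningfully faster may be drawn only if the sponsor justifies a margin in advance and the CI lies below it. A CI wholly between zero and the margin should be reported as faster, but by less than the margin, which keeps it consistent with the reading of a significant decrease in section 5.0 (Interpretation). The documents supply no margin, and none is proposed here.

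**Cost.** Text edits and some extra analysis, with no added patients or procedures. The downside is that many trials with no true gain will be reported as inconclusive. Without a margin this is nearly all of them, about 95% with exact timing. Against a purely illustrative 1-minute margin, exact timing would exclude the margin in 75% of null trials. An interval-censored normal model on 5-minute readings would do so in only about 22–43% (null means 5/6/6 and 5/7/7), and its CI would lean on the assumed distribution because nearly all times fall in two intervals.

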5.0 INTERPRETATION OF EXPECTED RESULTS

06_18_2014

If we see a significant decrease in time to achieve a T₁₀ dermatome level with the bupivacaine and lidocaine mixture compared to the bupivacaine only solution, then that would imply that the addition of the lidocaine did speed up the onset of action of the LA solution we used to activate the epidural. We would also need to account for each LA solution's side effect profile. By measuring the incidence of hypotension and degree of motor blockade, we will be able to determine if one solution's side effect profile is more favorable. By determining the advantages vs. disadvantages of each solution, we would be able to recommend the most ideal LA solution of those studied as the solution best suited for activation of labor epidurals.

5.0 ELIGIBILITY & EXCLUSION CRITERIA

Pregnant patients over the age of 18 who are scheduled for an induction of labor and request an epidural are eligible for the study.

Exclusion criteria are: age <18, allergy to the drug or drug class, preexisting neuropathy, history of back pain prior to pregnancy or history of back surgery, history of chronic opioid use, history of hypertension or hypertensive disorders of pregnancy, congenital or acquired cardiac disease, and contraindication to epidural placement (patient refusal, severe coagulopathy, infection at site of epidural needle insertion, severe hypovolemia)

6.0 RANDOMIZATION/RECRUITMENT PROCEDURES

Patients who are admitted to the labor and delivery (L&D) suite at the Women and Infants' Center (WIC) for induction of labor will be approached about recruitment into the study. The recruitment process will begin prior to any obstetric intervention that may induce pain or altered mental status to the patient.

As this will be a double-blinded study, the randomization process will be performed by someone other than the investigator gathering the data. Cards containing the LA to be given along with a code will be placed in a sealed envelope and numbered. There will be an equal number of patients randomized to each group. A card will be chosen by the anesthesia provider performing the procedure. The provider will administer the LA solution the patient is randomized to receive. The provider will write the code from the card on the data sheet. The code will be used to identify the LA solution given.

8.0 STUDY INTERVENTIONS/PROCEDURES

Our study will be a prospective, randomized, double-blind study comparing three commonly used methods to activate a labor epidural. These three solutions will be 10 mL of 0.125% bupivacaine (B), 10 mL of 1% lidocaine (L), and 5 mL of 0.125% bupivacaine plus 5 mL of 1% lidocaine (BL). The primary outcome of the study will be measurement of the time it takes to achieve an adequate anesthetic level (T₁₀) to control labor pains. Secondary outcomes include: the total level achieved, degree of motor blockade, incidence of maternal hypotension (>20% decline from baseline), the need for vasopressor use, the amount of vasopressor needed, and fetal

well-being (monitoring of FHR). Since LA will be required to produce our primary outcome, no group will receive a placebo. The three groups (B), (L), and (BL) will be compared to each other.

Pregnant patients who are admitted to the L&D floor at the WIC and have none of the above mentioned exclusion criteria will be approached about enrolling in the study. Informed consent will be obtained before any obstetric intervention occurs that might cause pain or altered mental status to the patient. Once the patient requests for her epidural to be placed, the investigator will be notified. Any qualified anesthesia provider will then place the labor epidural. Per our routine practice, the epidural will be placed in the L₂₋₃ or L₃₋₄ interspace, secured at plus 5 cm from the loss of resistance distance at the skin, and the routine test dose of 3 mL of 1.5% lidocaine with 1:200,000 epinephrine will be administered to rule out spinal or intravascular placement of the epidural catheter. After the epidural catheter is deemed safe to use (from a negative test dose), the anesthesia provider will administer the LA solution the patient has been randomized to receive: 10 mL (B), 10 mL (L), or 10 mL (BL), and the standard LA infusion will be connected to the epidural and started. The time that the LA bolus occurred will be marked as T₀. The patient's BP, HR, anesthetic level to pin prick and ice, degree of motor blockade, and FHR will be recorded at that time by the blinded investigator. Motor blockade will be tested by a modification of Bromage's scale where: 0 = the ability to maintain a leg lift for prolonged periods; 1 = the ability to lift legs briefly; 2 = the ability to bend knees; 3 = the ability to wiggle toes; 4 = no movement in lower extremities.³ Then at intervals of 5, 10, 15, and 20 minutes, the investigator will document the above mentioned data with the addition of any vasopressor (phenylephrine or ephedrine) required to treat maternal hypotension and the dose.

If, on administration of the test dose, the epidural catheter is believed to be intravascular (increase in HR > 20% above baseline) or spinal (an acute anesthetic level is noted by hip flexor weakness), then the catheter will be deemed not safe to use, and the patient will be removed from the study. The epidural catheter can be replaced by the anesthesia provider; however, since the data will be flawed from the initial positive test dose, the patient will not be allowed to participate in the study at that point. Also, if the patient does not receive an anesthetic level from the initial bolus plus infusion after 20 minutes, the epidural catheter will be documented as a failed catheter, and the patient will be removed from the study. The anesthesia provider will replace the epidural catheter in standard fashion if the patient requests to have it replaced.

The endpoint for our primary outcome will be the time it takes to achieve the T₁₀ level to pin prick, which should occur before 20 minutes; however, we will continue to monitor the patient throughout the 20 minute interval to determine the maximal spread of the LA (via measurement of the dermatome level by pin prick and ice), the degree of motor weakness, and if any hypotension occurs. During this time, the patient will have standard monitoring that all patients in labor receive: non-invasive BP and pulse recording and non-invasive FHR tracing. The L&D nurse, obstetricians, and anesthesiologists involved in the patient's care will deliver the same standard of care given to all patients on the L&D floor. Once the study is complete (after 20 minutes), the patient will continue to receive LA infusion through the epidural catheter throughout the remainder of labor and delivery. The anesthesia provider will continue to care for the patient throughout the patient's labor and delivery.

On average 5 to 10 patients are scheduled for induction each week. If 60% are consented for the study, then it should take approximately 3 months to enroll 45 patients.

Projected Overall Study Timeline

	Study Start-Up	Enrollment	Data Entry and Analysis	Study Write-Up
MM YYYY	08/2014			
MM YYYY		08/2014-11/2014		
MM YYYY			11/2014	12/2014

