2.0 BACKGROUND & RATIONALE

The most common and effective method for controlling labor pains is a local anesthetic infusion through a lumbar epidural.¹ To achieve adequate pain control during the first stage of labor – onset of contractions to complete cervical dilation – nerve fibers up to the T₁₀ dermatome must be anesthetized.¹ When a patient is in active labor and an epidural catheter is placed, the anesthesiologist must activate the epidural by administering LA through the epidural to promote spread of the LA in the epidural space to anesthetize the nerve fibers involved in the conduction of labor pains. The ideal LA to achieve this goal is one that would allow for the fastest onset to achieve quick pain relief with the fewest side effects. Common side effects of LA used in labor epidurals include maternal hypotension and motor blockade.³

Two commonly used LA to provide labor analgesia are bupivacaine and lidocaine. When low concentrations – 0.125% bupivacaine and 1% lidocaine – are used for labor analgesia, both of these LA can be administered safely with very little concern of major adverse effects associated with LA toxicity. However, more common side effects such as maternal hypotension requiring vasopressor therapy and motor blockade can often occur.³

Though both are amide LA, bupivacaine and lidocaine display different properties that give each an advantage in certain situations. Lidocaine's onset of action is faster than that of bupivacaine's (5-15 vs. 10-20 minutes for epidural injection).¹ Whereas bupivacaine has a longer duration of action (180-300 vs. 60-180 minutes).¹ Through a sympathetically mediated veno- and vaso-dilation, both LA commonly cause hypotension. Although the time to develop hypotension was not noted, several studies have noted a higher incidence of hypotension with the administration of epidural lidocaine vs. bupivacaine.^{2,4}

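### Should the primary ANOVA adjust for the sensory level recorded at T0, after the lidocaine test dose?

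*Combined protocol and SAP*

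**What the plan says.** Before randomised treatment, section 8.0 has every patient receive a test dose: "the routine test dose of 3 mL of 1.5% lidocaine with 1:200,000 epinephrine will be administered". The catheter counts as misplaced in the spinal space, and the patient leaves the study, if "an acute anesthetic level is noted by hip flexor weakness". The study solution follows, the infusion is started, and the time of the bolus is called T0. The "anesthetic level to pin prick and ice, degree of motor blockade, and FHR will be recorded at that time by the blinded investigator".

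Section 4.0 describes the sequence similarly: "Once the study drug bolus has been given, the investigator will collect the data". Starting from T0, "data will then be collected 5, 10, 15, and 20 minutes after the bolus". The primary outcome is the time to a T10 level by pin prick.

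The analysis in section 11.0 is one sentence: "An ANOVA will be used to estimate the overall difference of the mean onset times between study groups". It names no covariate. The contrast that section 5.0 (Interpretation of Expected Results) sets out to interpret is onset "with the bupivacaine and lidocaine mixture compared to the bupivacaine only solution".

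**The concern.** The T0 level is measured with the same pin-prick test that defines the primary endpoint, although it is a dermatome and not a time. The test dose contains 3 mL x 15 mg/mL = 45 mg of lidocaine, so a patient could start with some block and reach T10 sooner whatever she was randomised to. A baseline measure of the trait under study is often prognostic. With 15 patients per arm, leaving out a prognostic variable that is already collected can waste precision.

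A second worry concerns timing. Both sections describe the reading after they describe the bolus, and neither says it is taken beforehand. If the level were used as a covariate but read after treatment had begun to act, adjusting for it could remove part of the treatment effect.

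At stake would be the precision of the primary comparison and, if someone did adjust, its validity.

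**Working it through.** **1. Inputs.** From section 11.0: means 5, 6 and 7 minutes, variance 1 (SD 1), alpha 0.05, f = 0.82, calculated N = 18, target N = 45 (15 per arm). From sections 4.0 and 8.0: readings at 0, 5, 10, 15 and 20 minutes. Not in the documents: the within-arm correlation r between T0 level and onset time (0 to 0.5 assumed), the share of patients with any block at T0, and which mean belongs to which arm (lidocaine L = 5, mixture BL = 6, bupivacaine B = 7 assumed).

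**2. The plan's own figure.** f = sqrt{[(5-6)² + (6-6)² + (7-6)²]/3}/1 = sqrt(2/3) = 0.816. Power comes from the noncentral F distribution with λ = N f² and (2, N-3) degrees of freedom. At N = 15 it is 70.2%. At N = 18, λ = 12 and power is 80.5%, so the stated N = 18 reproduces. At N = 45, λ = 30 and power is 99.85%.

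**3. Bias.** All patients get the same test dose before the study solution, and allocation is random. A block already present at T0 therefore adds within-arm variation and chance imbalance, both of which the ANOVA error term covers. It shifts no arm systematically.

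**4. Adjustment, onset times known exactly.** With one covariate, λ = 30/(1-r²) with (2, 41) degrees of freedom. Omnibus power is 99.85%, 99.89%, 99.93% and 99.99% at r = 0, 0.2, 0.3 and 0.5. At most 0.15 percentage points can be gained. For a pairwise difference, the ratio of adjusted to unadjusted variance is (1-r²)(1 + 1/(42-2)) = 1.025, 0.984, 0.933 and 0.769. It breaks even at r = sqrt(1 - 1/1.025) = 0.156.

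**5. Adjustment, readings every 5 minutes.** This is the planned schedule. Each true time is rounded up to the next reading. With the plan's inputs, half of L is recorded at 5 and half at 10 minutes, giving variance 25 x 0.5 x 0.5 = 6.25. For BL the share recorded at 5 minutes is Φ(-1) = 0.159, giving 25 x 0.159 x 0.841 = 3.34. For B it is Φ(-2) = 0.023, and the variance is 0.59. A single common slope fits such unequal arms poorly. Simulation (60,000 trials per setting, normally distributed covariate) gives:

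| Adjusted / unadjusted variance | r = 0 | 0.2 | 0.3 | 0.5 |
|---|---|---|---|---|
| BL vs B | 1.042 | 1.032 | 1.019 | 0.979 |
| BL vs L | 1.016 | 0.998 | 0.975 | 0.899 |
| B vs L | 1.024 | 1.010 | 0.992 | 0.934 |
| Omnibus power, adjusted (unadjusted 85.9%) | 85.7% | 86.4% | 87.3% | 89.9% |

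For BL vs B, adjustment loses precision until r is about 0.4.

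**6. Few patients with a block.** If 50% have no block at T0 (placed at the slow-onset end), the BL vs B ratios at r = 0.2, 0.3 and 0.5 are 1.021, 1.003 and 0.945. If 80% have none, they are 1.014, 0.995 and 0.934. The break-even is then near r = 0.3.

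**7. Wider spread.** Section 2.0 gives onset ranges for lidocaine and bupivacaine of "5-15 vs. 10-20 minutes for epidural injection". Reading these as mean ± 2 SD gives means 10 and 15 and SD 2.5. A BL mean of 12.5 is assumed. On 5-minute readings the BL vs B ratios at r = 0, 0.2, 0.3 and 0.5 are 1.028, 0.997, 0.960 and 0.843. Pairwise power goes from 61.8% unadjusted to 60.7%, 62.2%, 63.8% and 69.6%. If 80% have no block at T0, the ratios at r = 0.2, 0.3 and 0.5 are 1.012, 0.995 and 0.940.

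**8. Timing of the reading.** The level is tied to the time of the bolus. Given the onset ranges in section 2.0, a reading at that moment should carry little effect of the study solution. In any case, the planned ANOVA uses only the onset time, so the order of bolus and T0 reading changes no planned result.

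**The case for a change.** The best case for adjusting is that the level costs nothing extra to collect, the arms are small, and the exact-time power of 99.85% is flattering. On the planned readings, omnibus power is about 86% under the plan's means, so there is less precision to spare. At r = 0.5 adjustment would lift it to about 90%, and in the wider-spread scenario it would cut the BL vs B variance by about 16%. The price is a few sentences in the protocol and, if the covariate proves useless, about 2.5-4% more variance for BL vs B.

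Those figures stand, but they need a strong correlation that the documents do not supply. The wider-spread result also needs a mixture mean that they do not give. No section says that any patient has a sensory level at T0, and removing patients with hip-flexor weakness after the test dose may narrow whatever spread there is. Prespecifying the covariate and dropping it when nearly all patients have no block would need a cut-off, for which the documents offer no basis.

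Two further points stand. An explicit statement that the T0 level is read before the bolus would be clearer. Anyone who did want to adjust would need that statement, and would need to fix the choice before unblinding. Neither makes the present analysis wrong.

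**Conclusion.** The concern does not hold. The facts behind it are right: a level is recorded at T0, it is not stated to be pre-bolus, and the ANOVA does not use it. Leaving out a baseline covariate is nevertheless a legitimate choice in a randomised comparison, and no figure, rule or analysis in the plan is wrong because of it.

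Adjustment is not shown to be an improvement either. For the contrast that section 5.0 interprets, on the planned readings and with the plan's own inputs, the variance changes by +4% to -2% for r from 0 to 0.5. The larger gains depend on r near 0.5 together with exact times or a wider spread than section 11.0 assumes.

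These sizes rest on the assumed r, the assumed assignment of means to arms, and normally distributed onset times rounded up to the next reading. The conclusion is limited to this covariate. It does not clear the ANOVA of separate questions, such as the coarse 5-minute readings with their unequal variances, patients who do not reach T10 by 20 minutes, or the removal of failed catheters after randomisation.
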